Title: Smell, voice and nasal swabs as markers for neurodegenerative disorders
PI: [name]. MSPH; [name]
Site: University of Arkansas for Medical Sciences

Specific Aims

The specific aims of the study are:

- Aim 1: Determine if smell, voice or vocal cord dysfunction serves as a reliable markers to distinguish between neurodegenerative disorders or among subjects with and those without neurodegenerative disorders.
- Aim 2: Determine if nasal swabs can provide an adequate sample for evaluation using cytology and immunohistochemistry for alpha-synuclein, A-beta and p-tau staining.
- Aim 3: Measure cellular levels of IL-1 a/b protein and mRNA levels and genotyping of apo-E4 alleles on the nasal mucosal swab samples.
- Aim 4: Evaluate if IHC and neuro-inflammatory marker levels correlate with severity of impairment in various cognitive or motor domains based on neuropsychological and motor scores, or olfactory impairment based on UPSIT scores.

Study Population

This is a prospective cross-sectional study of subjects with, or at risk of neurodegenerative disorders. Initial recruitment goal is for 60 subjects:

- Twenty people with Parkinson's Disease requiring evaluation of voice dysfunction by an Ear, Nose, and Throat (ENT) doctor
- Twenty people with other neurodegenerative disorders requiring evaluation of voice dysfunction by an ENT doctor.
- Twenty people with voice tremor and/or presbylarynx, but no evidence of Parkinson's other neurodegenerative disease, requiring evaluation of voice dysfunction by an ENT doctor.

Subjects will be recruited from the population of patients with neurodegenerative disorders (seen in the UAMS Neurology Clinic) or presbylarynx and/or voice tremor patients scheduled to undergo routine voice and laryngeal assessments as part of required clinical care for problems with voice and swallowing in the UAMS ENT Clinic.

Inclusion Criteria

- Diagnosed with idiopathic Parkinson's disease, progressive supranuclear palsy, Alzheimer's disease or Mild Cognitive Impairment based on consensus criteria, or suspicion of presbylarynx based on clinical evaluation.
- Require evaluation of voice dysfunction by an ENT doctor given symptoms of impaired voice volume or quality

Title: Smell, voice and nasal swabs as markers for neurodegenerative disorders

PI: [name]. MSPH; [name]

Site: University of Arkansas for Medical Sciences

- Age \geq 18 years-old to \leq 90-years old.

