De-identified OM samples and linked accompanying study data (including diagnostic certainty, motor and cognitive scores as well as smell testing data from study related procedures) will be stored for future research, and may be shared, de-identified, with other researchers at or outside UAMS, provided the subjects have given their written informed consent. Regarding the genotyping of apo-E4, results will not be shared with the study subjects. There exist several uncertainties about the reliability of the small sample and we do not intend to validate the results against a traditional method since this is a proof of concept pilot study.

Subjects can withdraw their consent and require destruction of their samples/data to prevent their use in future research by sending a written request to Drs. [name] or [name].

Data Analysis

As a first pass, frequency distributions and cross tabulations will be obtained to look at the data. Counts of missing data will be obtained. The distributions will be looked at for heaping, skewness and general amenability to analysis. We will compare the individuals with Parkinson's disease to those with presbylarynx or other degenerative disorders to look for any demographic differences. Cross tabulations will be done between "independent" (diagnosis of Parkinson's disease versus presbylarynx or other degenerative disorders) and "dependent" variables including abnormalities on laryngoscopy or stroboscopy, performance on smell identification test as both a continuous measure, and when classified into hyposmia and anosmia based on age and gender expected norms.

Title: Smell, voice and nasal swabs as markers for neurodegenerative disorders
PI: [name]. MSPH; [name]
Site: University of Arkansas for Medical Sciences

Additionally, we will look at the presence of histopathological markers for inflammation and misfolded protein deposition by potential confounding variables like age, gender, duration of disease, treatment characteristics at baseline and performance on smell testing etc. If needed, analyses will be repeated using stratification to investigate the effect modification by age, gender and time since diagnosis of Parkinson Disease, etc. Since these are preliminary analyses to determine effect size estimates to help power future studies, a power sizes cannot be estimated at this time.

Ethical Considerations

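### Group contrasts for continuous UPSIT and laryngeal findings are stated as crude cross tabulations, so effect sizes meant to power later studies may be confounded by age and gender

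*Protocol*

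**What the plan says.** Aim 1 (Protocol, Specific Aims) asks whether smell, voice or vocal cord dysfunction "serves as a reliable markers to distinguish between neurodegenerative disorders or among subjects with and those without neurodegenerative disorders". The Data Analysis section then states:

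- **Opening step:** "As a first pass, frequency distributions and cross tabulations will be obtained to look at the data".
- **Baseline comparison:** the groups are compared "to look for any demographic differences". No action is tied to the result.
- **Contrast:** cross tabulation of "diagnosis of Parkinson's disease versus presbylarynx or other degenerative disorders" against abnormalities on laryngoscopy or stroboscopy and against "performance on smell identification test as both a continuous measure, and when classified into hyposmia and anosmia based on age and gender expected norms".
- **Tissue markers:** histopathological markers are looked at "by potential confounding variables like age, gender, duration of disease", among other variables.
- **Further step:** "If needed, analyses will be repeated using stratification to investigate the effect modification by age, gender and time since diagnosis of Parkinson Disease".
- **Purpose:** the results are "preliminary analyses to determine effect size estimates to help power future studies".

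Study Population sets three groups of 20: Parkinson's disease, other neurodegenerative disorders, and voice tremor and/or presbylarynx. Inclusion Criteria allow ages 18 to 90, and no matching is stated. Laryngeal evaluation describes presbylarynx as ageing of the larynx. Smell Testing says that UPSIT has age-based norms. Demographics lists age and gender among the data collected.

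**The concern.** The three groups are formed by diagnosis, not by allocation, and one is recruited partly for a condition that the protocol itself ties to age. If the groups differ in age or gender, a crude difference in UPSIT score or in the frequency of laryngeal abnormality combines disease with age and gender.

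Stratifying to look for effect modification asks whether the group difference varies with age. It does not ask what the difference would be at equal age. The effect size is the stated product of the study, and its confidence interval shows sampling error only. Whoever plans the next study from that interval would not see the bias.

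**Working it through.** **1. What is stated for each outcome**

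| Outcome in Data Analysis | Handling of age and gender |
|---|---|
| Hyposmia/anosmia class | Built into the norms |
| Continuous UPSIT | Optional stratification only |
| Laryngoscopy/stroboscopy findings | Optional stratification only |
| Histopathological markers | Age and gender listed as potential confounders |

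The middle two rows are the gap. Time since Parkinson's diagnosis, the third stratifier, does not exist in the other two groups and so cannot adjust a between-group contrast.

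**2. The plan's own figure.** 3 x 20 = 60 agrees with the recruitment goal. No alpha, SD, effect size or power is given, so nothing else can be reproduced.

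**3. Size of the possible bias.** The inputs are assumptions, not in the protocol: age-outcome correlation r of 0.2-0.5; age gap g of 0-1 SD, in either direction, in the comparison group only; linear age effect; no true difference. The bias in the standardised difference is r x g.

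- Parkinson's v comparison group (20 v 20): 0.3 x 0.5 = 0.15; 0.5 x 0.5 = 0.25; 0.5 x 1 = 0.50; zero if g = 0.
- Parkinson's v the other two groups pooled (20 v 40): half of r x g, so at most 0.25.

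**4. Coverage of the crude 95% interval.** Coverage = Phi(1.96 - b/SE) - Phi(-1.96 - b/SE).

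- 20 v 20, SE = sqrt(1/20 + 1/20) = 0.316: 95%, 92%, 88% and 65% for b = 0, 0.15, 0.25 and 0.50.
- 20 v 40, SE = sqrt(1/20 + 1/40) = 0.274: 93% for b = 0.125 and 85% for b = 0.25.

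For comparison, the 95% half-width is 1.96 x 0.316 = 0.62 SD for 20 v 20 and 1.96 x 0.274 = 0.54 SD for 20 v 40. Sampling error exceeds the assumed bias throughout.

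**5. Would the optional stratification repair it?** In simulation (6,000 datasets per scenario, three groups of 20), pooling over two age bands left 0.19 of a 0.50 SD bias, and 36-40% across scenarios. It helps, but incompletely, and the protocol states no pooled estimate. Read stratum by stratum, an even split gives 10 v 10 and a half-width of 1.96 x sqrt(2/10) = 0.88 SD.

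**6. What adjustment does.** In the same simulations, a model with group, continuous age and gender left about 0.00 SD. Its SE was about 0.88 to 1.10 times the crude SE for gaps up to 1 SD, and 1.15 times at 2 SD. The zero holds because the data were generated from that model form. Two departures were checked:

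- Age effect only above the Parkinson's group mean age, r = 0.5: with a 1 SD gap, crude bias 0.68, linear adjustment 0.07, with age squared 0.01. With a 2 SD gap: 1.61, 0.29 and 0.11.
- Age slope 0 in Parkinson's and 0.5 in the other groups, 1 SD gap: the common-slope model left 0.16 SD at the Parkinson's mean age.

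**7. Consequence for the next study.** With an assumed true difference of 0.8 SD, required size scales as (0.8/(0.8 + b))^2. For b = +0.15 or -0.15 this gives 0.71 or 1.5 times the right size; for b = +0.25 or -0.25, 0.58 or 2.1 times.

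**The case against.** **It is a pilot's first look, and a separate analysis plan may name covariates.** This has weight. The section opens as a first pass, rules out no later model and never says that the crude figures alone will be carried forward. A continuous score cannot literally be cross-tabulated, so the wording may describe data inspection. But the protocol does state a method for these contrasts and does say what stratification is for. Followed as written, it yields crude estimates. The point rests on that text, not on absent detail.

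**Partial safeguards exist.** Demographic differences are checked, the hyposmia/anosmia classes are normed, and stratification by age and gender would give some control of confounding if it were run. All of this stands. A reader might infer that the plan ignores age altogether; it does not.

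**The protocol names age and gender as confounders.** A reader might take this as an admission covering smell and laryngeal outcomes. The phrase is attached only to the histopathological markers. The case for age mattering here comes from the UPSIT norms, the description of presbylarynx, the 18-to-90 range and the absence of stated matching.

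**Stratification is unworkable at five per cell.** A reader might infer this by crossing two age bands with gender. The protocol lists the stratifiers but does not say that they are crossed, so the argument should not rest on it.

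**Sampling error dominates.** True: at an observed 0.8 SD with 20 v 20, the 95% interval (0.16 to 1.44) alone gives size ratios from 0.31 to 26. That uncertainty is visible in the interval; the bias is not.

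**Conclusion.** The point holds as a possibility that the stated method leaves open. Crude effect sizes for continuous UPSIT and laryngeal findings may be confounded by age and gender, and the only stated remedy is optional and directed at effect modification.

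The sizes in steps 3 and 4 of the working rest wholly on the assumed correlations and age gaps. A reader might infer that the estimates are biased, or biased by half an SD. The protocol supports neither: it gives no group ages, the range includes zero, and the direction is unknown. The upper end needs r = 0.5, a full 1 SD gap and the 20 v 20 contrast. The section's wording can equally be read as 20 v 40, where the assumed maximum is half as large, provided only the comparison group differs in age.

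Nor does it follow that adjustment removes all bias. It relies on age overlap and a reasonable model form, and it cannot undo the selection of the comparison group on a laryngeal or voice condition, which for laryngeal findings may outweigh age. The change is worth making but is not critical: age and gender are collected, so nothing would be irrecoverably lost.

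**What to change.** In Data Analysis:

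- Beside each crude contrast for continuous UPSIT and laryngeal or voice outcomes, report an estimate with 95% CI adjusted for continuous age and gender, with diagnostic group at three levels. Use a linear model for continuous outcomes (or age- and gender-normed UPSIT scores) and penalised or exact logistic regression for binary laryngeal findings.
- Leave the normed hyposmia/anosmia classes as they are.
- Show the age distribution by group, and add an age-squared term as a check.
- Keep stratified tables as exploratory for effect modification, and use time since Parkinson's diagnosis only within the Parkinson's group.
- State as limitations that adjustment reduces bias only with adequate age overlap and a reasonable model form, and that it does not remove selection of the comparison group on a laryngeal or voice condition.

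Cost: wording only, since both covariates are already collected. The model spends two degrees of freedom, and the change in standard error is the one given in step 6: a small gain or a small loss for age gaps up to 1 SD.
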